4.3 Intervention

All eligible patients, meeting inclusion and exclusion criteria, who provide informed consent and voluntarily agree to participation in this psychotherapy intervention study will be randomly assigned to one of three study arms: the two psychotherapy interventions described below or the enhanced usual care condition. Individual sessions of either IMCP or ISP will be held in the MSKCC Department of Psychiatry and Behavioral Sciences ambulatory care facility: The MSK Counseling Center, MSKCC [name]. In rare cases therapist may see patients in other treatment facilities at MSKCC such as the Breast Center, Outpatient Treatment Center, or Inpatient Hospital if circumstances such as severe illness preclude the patient from traveling to the MSKCC counseling center. On rare occasions at the discretion of the P.I. and individual therapist, participants who become severely ill or hospitalized may be permitted to participate in individuals through teleconference in order to maximize therapeutic benefits to participants and minimize attrition. Participants will attend individual sessions weekly for 60 minutes. There will be seven individual sessions with an outside window of 14 weeks. Ideally, the psychotherapy will be completed in 7 weekly sessions. However, we have allotted a window of approximately 14 weeks to complete the 7 sessions, allowing for occasional meetings every 2 weeks in the event of medical illness in this advanced cancer population. The follow-up assessments will be 8 weeks after the last session.

Individual Meaning-Centered Psychotherapy (IMCP): IMCP is based on the principles of Viktor Frankl's Logotherapy, and is designed to help patients with advanced cancer sustain or enhance a sense of meaning, peace and purpose in their lives even as they approach the end of life. IMCP is structured as a 7-session (1-hour weekly sessions) individual intervention that utilizes a mixture of didactics, discussion and experiential exercises that focus around particular themes related to meaning and advanced cancer (See Appendices I & J for IMCP Treatment Manual and IMCP Participant Manual). The session themes include:

- Session 1 – Concepts and Sources of Meaning
- Session 2 – Cancer and Meaning: Identity Before & After Cancer Diagnosis
- Session 3 – Historical Sources of Meaning: Legacy (past, present and future)
- Session 4 – Attitudinal Sources of Meaning: Encountering Life's Limitations
- Session 5 – Creative Sources of Meaning: Creativity & Responsibility
- Session 6 – Experiential Sources of Meaning: Connecting with Life via Beauty, Love & Humor

- Session 7 – Transitions: Reflection, and Hopes for the Future

Patients are assigned readings (i.e. Man's Search for Meaning by Victor Frankl) and homework that are specific to each session's theme and which are utilized in each session. Participants may also complete an optional Legacy Project outside of the group based on these themes and discussion (ie. autobiography, artwork, photo album, family history, etc). While this intervention is primarily psychoeducational with the focus of each session on issues of meaning and purpose in life in the face of advanced cancer/limited prognosis, elements of support and expression of emotion are inevitable, but limited by the focus on experiential exercises, didactics and discussions related to themes focusing on meaning).

Individual Supportive Psychotherapy (ISP): The ISP intervention (see Appendix K for ISP Treatment Manual), utilized as the comparison treatment condition in this study, is adapted from the Supportive Group Psychotherapy manualized intervention developed by David Payne (1997) and adapted by Drs. [name], [name] and colleagues into the ISP manualized intervention. This intervention is a 7-session individual supportive psychotherapy utilizing an approach to supportive psychotherapy based on models described by Rogers (1951, 1980) and Bloch (1996). The essential components of supportive psychotherapy are integrated into this manualized intervention, including: reassurance, explanation, guidance, suggestion, encouragement, affecting changes in patient's environment, and permission for catharsis (Bloch, 1996). The ISP therapeutic process emphasizes Rogerian person-centered concepts: genuineness, unconditional positive regard, and empathic understanding. The ISP therapeutic content emphasizes maintaining focus on cancer, supporting patients in the here and now, fostering expression of emotion and discussion of difficult topics, and creating a sense of being understood (Payne, et al., 1997). The manual also contains specific instructions on how to avoid therapeutic techniques that are not exclusively supportive (e.g., interpersonal therapy, cognitive-behavioral therapy, meaning-centered therapy).

Enhanced Usual Care (EUC): The use of a usual care condition to increase the methodological rigor of this randomized controlled trial must be balanced with the need for beneficence and preventing harm in the care of patient participants. We are therefore including what we refer to as an —enhanced— usual care arm to this randomized controlled trial to address the ethical issues raised by utilizing a usual care condition in a vulnerable advanced cancer population. The —enhancement— to usual care in this study involves the inclusion of screening and targeted referral components as suggested by Reynolds et al. (2001). Participants will receive feedback about their level of distress (based on the DT administered at screening) and given appropriate targeted referrals based on levels of distress and problem areas endorsed. Participants will be given a letter with a list of appropriate referrals. Several referrals may be made based on identified problem areas, using the following guidelines:

- —Practical Problems—- Social Work on their disease management team
- —Family Problems—- Family Clinic at MSKCC Counseling Center
- —Emotional Problems—- MSKCC Counseling Center
- —Spiritual/Religious Concern—- Pastoral Care Counseling Services
- —Physical Problems—- MSKCC physician or MSKCC Palliative Care Service

In addition, patients may be offered community resources as well. Research assistants conducting the screening and providing feedback and referrals will be trained in the NCCN guidelines for distress management (NCCN, 2009; see Appendix G). Regardless of whether they indicate significant distress or any problem areas patients in the EUC will all be provided with informational brochures on psychosocial services available at MSKCC (i.e., the MSKCC Counseling Center Services Guide for Patients [MSKCC, 2007], psychoeducational materials (see

Appendix H) and a book entitled —The Human Side of Cancer|| by [name]. EUC patients will be closely monitored at each assessment point for significant distress and highly distressed patients (i.e. 8 or above on DT or endorsement of suicidal ideation on BDI) will be referred to the counseling center or contacted by the PI for further assessment as needed.

Selection, Training and Supervision of Leaders: We have carefully considered the selection of therapists and intensive training and supervision of our treatment providers. The manualized research interventions for this protocol, IMCP and ISP, are highly structured, as therapists are provided with an outline of content for all study sessions. Therefore, we determined that therapists must have, at minimum, a Masters degree in Mental Health Counseling, social work, or psychology to qualify for consideration as an interventionist on this study. Clinicians with greater experience and more advanced skills will also be considered for the therapist role on this study. Therapists will be assigned to either the IMCP or ISP arms to maximize the differentiation between the formats. Supervision and training for IMCP and ISP will be conducted by the P.I. or Co-Investigator in charge of each treatment arm.

All research study counselors are either MSKCC-employed mental health clinicians or non-MSKCC employed mental health clinicians contracted to work on specific research studies. We use the services of non-MSKCC mental health clinicians as study counselors so that we can best accommodate participant schedules and availability to attend the study sessions.

All study interventionists will undergo extensive training in either IMCP or ISP, by the P.I. or Co-Investigator. Although some MSKCC clinicians are already experienced in providing IMCP or ISP from our pilot study period, the P.I. and Co-Investigator will lead periodic intensive training workshops in the delivery of these interventions for each distinct intervention therapists. All therapists will be provided with a copy of the treatment manual for the intervention they will be providing, describing in detail the philosophy, format, and techniques involved in the intervention. These training workshops will focus on the acquisition of skills in the conduct of each intervention. We will also provide —booster|| training to maintain standardized delivery of both treatment conditions to prevent —provider drift.|| To reinforce standardized treatment delivery, the P.I. or Co-Investigator in charge of the treatment arm will lead supervision sessions for the different treatment providers.

Therapists will be trained on an as needed basis for the duration of the study. If needed some therapists in training may conduct 1-2 training cases with patients who are not eligible to participate in the study due to stage of cancer, low distress or past participation. Therapists will receive intensive supervision and the therapist's competency in the intervention will be assessed to determine if they are ready to be study therapists. Participants who are consented as training cases will not be randomized and will not complete any assessments. Data collected on training cases will be used for training and supervision purposes on this study only. These records will not be shown outside of the study supervisors, therapist in training, and staff. Training will be approximately 7-14 weeks to allow for trainees to complete the 7 sessions of the intervention. The audio-recordings from the training cases will be kept for the duration of the study to train future therapists and will be destroyed after the study is completed. Training participants will be offered reimbursement for travel expenses.

Adherence to Intervention Format: We will institute several —best practices|| to enhance and monitor treatment fidelity, which include: careful attention to the study design, selection, intensive training and supervision of treatment providers, delivery of treatment, receipt of treatment, and —real-life|| enactment of treatment skills. With regard to study design, we will compare two

intervention conditions (IMCP and ISP) that are equivalent with regard to the number, frequency and duration of sessions. We will monitor session attendance using a diary log with names and session dates to track percentage of attendance and to account for absenteeism and reasons for missed sessions. We will make every effort to deliver the full treatment, but we expect some variation in treatment delivery dose as well as treatment drop-out. Reasons for attrition will be assessed with an open-ended question for enrolled participants who withdraw. Drop-out reasons will be categorized and then judged by independent raters. To reduce likelihood of treatment contamination, each of the treatment conditions (IMCP and ISP) will be delivered by distinct treatment providers. We have developed comprehensive treatment manuals for IMCP and ISP (see Appendices I, J & K) to facilitate standardized delivery of the treatment sessions. Therapists will monitor attendance and homework completion as part of their process notes. We will also collect information about EUC utilization of resource referrals. Deviations from protocol will be recorded, and discussed regularly during supervision. We will also externally monitor treatment sessions, feedback sessions for the EUC arm, and provide feedback to interventionists.

Treatment Integrity/Adherence to Intervention Format: We will establish several procedures to monitor treatment protocol adherence and improve standardized delivery of the treatment. First, we have developed standardized treatment manuals for each of the treatment conditions (IMCP and ISP). To ensure that providers are adhering to the treatment protocol, we have developed a provider outline of intervention components for each treatment session, for both of the interventions that are included in each treatment manual. These checklists/outlines can be used to facilitate supervision. We have also developed —Treatment Integrity Coding Manuals (see Appendix L), adapted from [name] experience in developing treatment integrity assessment methodology in his work on Family Focused Grief Therapy (Chan et al. 2004), for each of the two interventions (IMCP, ISP). These —Treatment Integrity Manuals allow for independent raters to evaluate each session of both interventions for treatment adherence in terms of process and content. The MSKCC Department of Psychiatry and Behavioral Sciences will have available two psychotherapy conference and consult rooms with 2-way mirrors, audiotape recording capabilities which will enhance our ability to provide supervision, training and treatment integrity. All sessions will be audio-taped, with prior consent of the participants. A random sample of about 15% of all recorded sessions (approximately 1 session per IMCP/ISP case) will be evaluated and rated for treatment integrity (utilizing the Treatment Integrity Coding Manual). To prevent against therapist drift, treatment integrity ratings will be conducted regularly throughout the period of therapy within the study. All raters will be given the opportunity to offer written comments/feedback to individual facilitators regarding the specific individual session to enhance continued training and supervision in these individual interventions. Raters will be blinded to the therapist but not to the intervention arm or the specific session within that treatment arm, and required to achieve >80% inter-rater reliability. We will also use a patient-generated measure of treatment adherence, the —Post-intervention Questionnaire, described in the Study Measures section.

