access to the de-identified data hosted by their servers for the purpose of ensuring the proper functioning of the database and the overall software system. REDCap is a tool for the creation of customized, secure data management systems including web-based data entry forms, reporting tools, and a full array of security features including user and group based privileges with a full audit trail of data manipulation and export procedures. REDCap is maintained on CTSC-owned servers that are kept in a locked server room with appropriate environmental modifications (e.g., special air conditioning), supported by an uninterrupted power supply, and backed up nightly with some backup tapes stored off-site. All connections to REDCap utilize encrypted (SSL-based) connections. Nationally, the REDCap software is developed, enhanced, and supported through a multi-institutional consortium led by the Vanderbilt University CTSA. Use of REDCap has been approved by the Department of Psychiatry & Behavioral Sciences' manager of IT Systems.

Subject Burden

In an effort to minimize patient burden, the assessment protocol has been designed to be as brief as possible in order to gather the required information. The assessment battery takes approximately one hour to complete, depending on the individual patient. Research staff will interrupt an assessment if a patient is fatigued or in significant pain. In an effort to ease patient burden, all self-report measures will be read to the patient if necessary.

Tests and Measures

Study participants will be assessed at baseline, midpoint, and follow-up assessments, using the following study measures (see Appendices A, C, D, E, & F for assessment questionnaires). The measures chosen have all been widely used with medically ill patients and have been used to study patients with cancer. In selecting these measures, an effort was made to limit subject burden. Assessments will be completed in person or if the patient is not able to complete the follow-up questionnaires in person, the research study team reserves the right to be able to mail or complete the questioners over the phone with the participant.

Screening for Eligibility Criteria:

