1. **Sociodemographic Questionnaire:** Sociodemographic information will be obtained at the pre-randomization time point consisting of questions concerning age, gender, ethnicity, education, employment history, marital status and household composition, and religious affiliation and practices. Significant medical and other life events which occur during the course of treatment and follow-up will be recorded for each patient. (5 minutes; T0)
2. **Distress Thermometer (DT):** The Distress Thermometer (Roth et al., 1998) is a single-item visual analog scale used to screen cancer patients for the presence of psychological distress with a 0-10 range. The National Cancer Center Network (NCCN) Clinical Practice Guidelines for Distress Management recommend use of the DT, along with a 34-item problem checklist (NCCN, 2003, 2009). An extensive research literature has documented the utility of the DT as a screening tool for oncology settings, and has identified a cut-off of 4 or greater for identifying clinically significant psychological distress (e.g., Grassi et al., 2009; Jacobsen et al., 2005). (2 minutes; T0, T2, T3)
3. **Karnofsky Performance Rating Scale (KPRS):** Observer-rated scale used by physicians to report patient's level of physical performance with a range of 0-100. (Karnofsky & Buchenal, 1949; Coscarelli-Schag, 1984). KPRS is rated upon admission screening and at each assessment. (1 minute; T0, T3, T4)

Health Status Measures:

1. Health Status Interview (HS): Extent of disease, degree of medical co-morbidity, concomitant therapies, and significant medical events occurring during the study will be recorded for each patient. (5 minutes; T1)

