2. Schedule of Attitudes towards Hastened Death (SAHD): This 20-item questionnaire (range 0-20) was developed by the responsible investigators as a self-report measure of interest in hastened death ([name], [name], et al., 1999; 2000). This measure has been administered to more than 300 patients with terminal cancer and HIV/AIDS, and has demonstrated high levels of reliability (alpha coefficient=.88 and median item-total

correlation=.43). In addition, the SAHD has demonstrated concurrent validity, correlating 0.88 with the clinician-rated Desire for Death Rating Scale (Chochinov et al., 1995), and somewhat more modestly ($r=.47$ to 0.65) with measures of depression and overall psychological distress. This range of scores and pattern of correlations with measure of depression is consistent with previous research (e.g., Chochinov et al., 1995; [name] et al., 2001). (under 5 minutes; T1, T2, T3, T4)

3. Hopelessness Assessment in Illness (HAI): The Hopelessness Assessment in Illness scale (HAI) is a brief, 8-item questionnaire specifically developed through a R01-funded research study ([name], P.I.; [name], Co-P.I.) to assess hopelessness in cancer patients with advanced disease and terminal illness (range 0-16). ([name] et al., in press). The HAI has demonstrated a high degree of internal consistency (coefficient alpha above .80) and construct validity (e.g., a correlation of .74 with clinical ratings of hopelessness). The HAI demonstrated incremental validity over and above existing measures of hopelessness, such as the Beck Hopelessness Scale, which our group has used in previous research studies. (under 5 minutes; T1, T2, T3, T4)
4. McGill Quality of Life Questionnaire (MQOL): A brief, self-report instrument designed to assess various domains of psychological, spiritual, and physical functioning among terminally ill patients (Cohen et al., 1995). Patients rate their current functioning on a scale of 0 to 10. The physical and psychological domains of the MQOL are highly correlated with other measures of quality of life, although the existential/spiritual domain assessed by this measure has not typically been included in other quality of life measures. This measure has demonstrated reliability (internal consistency $> .70$ for the subscales), and adequate levels of concurrent validity (e.g., correlation of .34 with the Spitzer Quality of Life Index) (under 5 minutes; T1, T2, T3, T4)

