8.0 TOXICITIES/SIDE EFFECTS

Minimal risk of psychological distress is posed by study questions that ask participants to identify their current problems. However, since study items were chosen to reflect what are likely to be

existing concerns, the present study is not expected to markedly increase participants' psychological distress above their routine concerns. Experienced personnel, trained in interviewing medically ill individuals, will administer all instruments, and will be supervised by the Principal Investigator or Project Coordinator. Participants' reactions will be observed and signs of significant distress will be followed up by the PI or study therapist with attention to presence of any serious psychological concerns. In the unlikely event of significant acute distress, participants will be referred to a staff member from the Department of Psychiatry and Behavioral Sciences. If a research participant indicates that s/he is acutely suicidal and poses a significant and acute risk of self-harm, this information will be shared with their attending physician so that timely and appropriate psychiatric assessment and care can be provided by the MSKCC Social Work or Psychiatry Service staff.

However, some subjects may become distressed or experience anxiety when discussing end-of-life care issues in the individual psychotherapy sessions or in response to filling out the self-report questionnaires that inquire about their illness, degree of depression, thoughts on end of life care, feelings of hopelessness, pain and physical symptoms, quality of life and social support. All patients will be monitored for severe distress and explicit suicidal ideation with plan or intent at each assessment point (including EUC). We will continue to utilize interviewers who have been trained to be sensitive to the nature of end-of-life care issues. When necessary, subjects who experience psychological distress related to filling out self-report questionnaires will be referred to appropriate care by the MSKCC Psychiatry Service.

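### The EUC referral trigger does not match the assessment schedule: its suicidal-ideation part has no listed instrument, and neither part is scheduled at T4

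*Combined protocol and SAP*

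**What the plan says.** All references are to the combined protocol and SAP.

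- **Purpose of the arm.** Section 4.3 says that a usual-care control "must be balanced with the need for beneficence and preventing harm in the care of patient participants". The enhanced arm is offered as the answer.
- **The rule.** Section 4.3 states that "EUC patients will be closely monitored at each assessment point for significant distress". It then sets the trigger, under which "highly distressed patients (i.e. 8 or above on DT or endorsement of suicidal ideation on BDI) will be referred to the counseling center"; the alternative is contact from the principal investigator, as needed. The two conditions are joined by *or*.
- **The measures.** Section 7.1 introduces its list with "Study participants will be assessed at baseline, midpoint, and follow-up assessments, using the following study measures". The DT entry carries the time tag "2 minutes; T0, T2, T3". The BDI has no entry.
- **General safety text.** Section 8.0 extends monitoring for severe distress, and for suicidal ideation with plan or intent, to every assessment in all arms. It names no instrument or threshold. It adds that participants' "reactions will be observed and signs of significant distress will be followed up by the PI or study therapist".
- **Reporting.** Section 14.3 makes expressed ideation with plan or intent a serious adverse event.

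**The concern.** The rule depends on two instruments. One is missing from the list of measures, and the other is not scheduled at the last assessment. Staff who follow Section 7.1 to the letter can apply the DT condition at T2 and T3. They have no listed means of applying the ideation condition at any visit, and at T4 they have nothing to apply.

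This rule is part of the protection that Section 4.3 relies on to justify a usual-care control in distressed patients with advanced cancer. IMCP and ISP patients have up to seven sessions with a therapist, whereas EUC patients meet the study mainly through the assessments. T4 comes 8 to 12 weeks after T3, so the earlier DT readings are out of date by then. What is at stake is an EUC patient who meets the intended criterion and is not flagged by it.

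**Working it through.** The plan gives no figure for this point. The check sets the rule beside the schedule and then counts the assessments affected.

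**1. Is the BDI scheduled?** In the supplied text the BDI appears only in the Section 4.3 rule. It is absent from the Section 7.1 measures, from the primary outcomes in Sections 9.1 and 11.0 (LAP-R, FACIT-Sp, HADS, SAHD, HAI, MQOL) and from the references. The other Beck instrument named, the Beck Hopelessness Scale, belongs to the group's earlier studies. The nearest listed measure is the SAHD (T1 to T4), which "was developed by the responsible investigators as a self-report measure of interest in hastened death". No cut-off or review rule is attached to it, nor to the HADS, HAI or MSAS.

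**2. Coverage by time point, on the written schedule.**

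| Assessment | DT of 8 or above | Ideation on BDI |
|---|---|---|
| T0 (screening) | scheduled | not listed |
| T1 | not scheduled; T0 reading is recent | not listed |
| T2 | scheduled | not listed |
| T3 | scheduled | not listed |
| T4 | not scheduled | not listed |

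The timeline in Section 9.1 puts T0 at week 0 and T1 at week 1, so the T0 reading largely serves for T1. Section 4.2 does allow up to four weeks between randomization and the start of the intervention, so the reading can be somewhat older. No such substitute exists for T4. As extracted, the same timeline marks EUC referral facilitation at weeks 1, 4 and 7 and not at week 15, which agrees with the T4 gap.

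**3. Size of the T4 gap.** Section 11.0 gives 138 patients per arm at baseline, 104 at post-intervention and 90 at follow-up. T2 is not stated; it is assumed to lie between 104 and 138.

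- Planned EUC assessments, T1 to T4, with T2 = 104: 138 + 104 + 104 + 90 = 436.
- With T2 = 138: 138 + 138 + 104 + 90 = 470.
- T4 share: 90/470 = 0.191 to 90/436 = 0.206, that is 19% to 21%.

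**The case against.** The strongest reply is that Section 7.1 is not a complete list, so absence from it proves little. Section 6.0 names a Mini Mental at screening that Section 7.1 does not describe. Time tags are also loose: the Karnofsky entry says it is rated at each assessment but is tagged T0, T3 and T4. The questionnaires are in Appendices C to F, which are not shown. Section 8.0 says that earlier studies with a very similar battery examined suicidal ideation, which suggests, without proving, that this battery does too. This stands as a limit on the point. If the appendices contain the BDI, the first part reduces to an omission from Section 7.1. If they contain the DT at T4, the tag is what needs correcting. Either way the written rule and the written schedule disagree.

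Three stronger readings are tempting, and the documents do not support them.

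- *The trigger cannot be operated at all.* The conditions are alternatives, and the DT condition is scheduled at T2 and T3.
- *About half of EUC assessments are uncovered.* Counting T1 as well gives (138 + 90)/470 = 49% to (138 + 90)/436 = 52%. That ignores the screening DT taken shortly before T1.
- *Suicidality is unmonitored, so serious adverse events will be missed.* Section 8.0 provides for observation and referral. Sections 8.0 and 14.1 expect that research assessments can reveal serious suicidality and say who is then told. Section 13.1 identifies adverse events through clinical assessment of each participant. Section 14.3 turns on expressed ideation, which does not require a questionnaire item.

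A reader might also object that assessments may be mailed (Section 4.2), where reactions cannot be observed. That is true, but how quickly returned forms are read is an operating-procedure matter and not a contradiction in the plan.

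**Conclusion.** The point holds as a mismatch between the EUC referral rule and the written schedule. The ideation condition has no listed instrument at T1 to T4, and neither condition is scheduled at T4, which affects about 90 EUC patients or 19% to 21% of planned EUC assessments. The DT condition is workable at T2 and T3, and T1 is largely covered by screening.

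The size rests on the retention planned in Section 11.0 and on the assumed range for T2. The finding itself rests on the Section 7.1 list and its time tags, and could narrow once Appendices C to F are checked. The documents do not allow an estimate of how many patients would meet the trigger at T4. This is a safety-procedure correction: no efficacy analysis, sample size or error rate is affected.

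**What to change.** 1. In Section 4.3, replace the BDI with one named suicidal-ideation item given at T1, T2, T3 and T4, and list it in Section 7.1. If the BDI is already in Appendices C to F, list it in Section 7.1 with its time points instead.
2. Add the DT at T4, and state that the screening DT serves as the trigger at T1.
3. Before T3, keep the referral rule for a DT of 8 or above in EUC only, as written. Extending it to all arms would prompt clinical reviews at T2 in IMCP and ISP and could add co-intervention before the primary time point.

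**Cost.** The changes are short text edits, one added item and about 2 minutes per patient at T4. That is 90 × 2 = 180 minutes (3 hours) for EUC, or 3 × 90 × 2 = 540 minutes (9 hours) if the DT is given in all arms to keep the battery the same. Clinicians must follow up positives, which the plan already intends. The documents give no rate; if 5% to 15% of EUC patients scored 8 or above at T4 (an assumption), that is 90 × 0.05 = 4.5 to 90 × 0.15 = 13.5 patients. T4 is the last assessment, so referrals prompted by its DT cannot alter T3 or T4 outcomes. The ideation item at T1 to T3 may prompt a few extra referrals, in line with the monitoring promised in Section 8.0.
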